6.1 Design

Parallel two-arm open-label individually randomised controlled trial with two co-primary endpoints, an internal pilot phase and group-sequential stopping rules for effectiveness and futility/safety. Participants will be randomised in a ratio of 1:1 to NEWS2 and local standard care or the PCT-guided assessment.

6.2 Setting

NHS Emergency Departments (EDs) in the UK. We have 6 sites (Leeds, Hull, Hampshire, Portsmouth and Brighton & Sussex NHS trusts) with Royal Liverpool University Hospital as the lead NHS site. We aim to recruit a maximum of 20 sites.

Site Inclusion Criteria

- NHS ED sites using NEWS2 (as recommended, not modified)
- Receive patients 16 years and over with suspected sepsis
- Willing to randomise patients to standard care (NEWS2) or NEWS2 + PCT algorithm guided therapy

7 Site and Investigator selection

This trial will be carried out at participating sites within the UK. All sites who are interested in participating in the trial will be required to complete a registration form to confirm that they have adequate resources and experience to conduct the trial.

Before any site can begin recruitment a Principal Investigator at each site must be identified. The following documents must be in place and copies sent to the PRONTO Trial email account (see contact details on page 4):

- The approval letter from the site's R&D Department, following submission of OID (Organisation Information Document) form and the UK local information pack.
- Favourable opinion of host care organisation/PI from Main Ethics committee.
- A signed Trial Site Agreement (PI, sponsor and site signatures).
- Current Curriculum Vitae and GCP training certificate of the Principal Investigator (PI).
- Completed Site Delegation Log, Signature Log and Roles and Responsibilities document.
- Full contact details for all host care organisation personnel involved, indicating preferred contact.
- A copy of the most recent approved version of the Participant Information Sheet(s) and Consent Form(s) on host care organisation headed paper.
- Returned copy of the Self-Evident Correction Log signed by the PI.

Upon receipt of all the above documents, the Trial Manager will send written confirmation to the Principal Investigator/lead Research Nurse detailing that the site is now ready to recruit participants into the trial. This letter/email must be filed in each site's Site File. Along with the written confirmation, the site should receive their trial materials and all the documents required to recruit into the Trial.

Occasionally during the trial, amendments may be made to the trial documentation listed above. CTR will issue the site with the latest version of the documents as soon as they become available. It is the responsibility of the CTR to ensure that they obtain local R&D approval for the new documents.

Site initiation will be by attendance at a PRONTO launch meeting or by teleconference if attendance of key personnel is unfeasible.

8 Participant selection

Participants are eligible for the trial if they meet all of the following inclusion criteria and none of the exclusion criteria apply. All queries about participant eligibility should be directed to the Trial Manager before randomisation/registration.

8.1 Inclusion criteria

Patients \geq 16 years presenting to the ED with suspected sepsis.

8.2 Exclusion criteria

- Currently on intravenous antibiotics.
- Current use of any chemotherapy agent associated with myeloablation/suppression.
- History of solid organ transplantation, allogeneic bone marrow or stem cell transplantation within 3 months prior to consent.
- Patients known to require urgent surgical intervention (within the course of current admission)

- Presence of an advance directive to withhold life-sustaining treatment (patients not wishing to receive Cardiopulmonary Resuscitation (CPR) may qualify provided they receive all other resuscitative measures e.g. respiratory support, fluid resuscitation).

9 Recruitment, screening and registration

9.1 Participant identification

Patients with suspected sepsis will be identified at ED triage. After initial NEWS2 and assessment according to current standard of care the eligibility criteria will be assessed and if no exclusion criteria apply, patients will be enrolled into the trial and randomised.

As a deferred consent model is being used patients and their relatives will be informed that a study is ongoing but a lengthy consent discussion will not be had so as not to delay treatment. Should the patient or consultee wish not to take part at this point, then the decision should be respected and the patient should not be enrolled into the trial. Patients who have given verbal consent will be randomised regardless of baseline NEWS2. See study flow chart for the process.

9.2 Screening logs

A screening log of all eligible and randomised patients will be kept at each site so that any biases from differential recruitment will be detected. When at site, logs may contain identifiable information but this **must** be redacted prior to being sent to the CTR. The screening log should be sent to the trial specific email address ([contact]) every month (see section 25 for further detail on data monitoring/quality assurance). Screening logs sent to the CTR that have not been redacted will be identified on receipt by the trial management team and appropriate measures will be taken to ensure site staff are aware of the requirement to redact information (monitoring and training). This will also be relayed during site set up training.

9.3 Informed consent

[figure not shown]
Research carried out in emergency situations is challenging in terms of obtaining consent. Emergency research is when treatment needs to be given urgently, and it is necessary to take urgent action for the purposes of the study. In some emergency situations people may lack capacity to give consent themselves and obtaining consent from a legal representative/consulting others is not reasonably practicable. Patients in this study will be very unwell and although they may self-refer themselves to the ED, they will not have the capacity to provide an informed decision with time to consider the trial in such a setting. In England and Wales, the law allows adults who lack capacity to take part in emergency research without prior consent from a legal representative or consulting others, if certain conditions are met (Medicines for Human Use (Clinical Trials) Amendment (No 2) Regulations SI 2006 2984, Mental Capacity Act s32) [6]. Given the requirement for rapid clinical assessment and treatment in our setting, for this study we will use a deferred consent model. Findings from a recent systematic review indicate that this deferred consent approach is broadly accepted by potential participants, clinicians and researchers for research in emergency settings [30].

Following enrolment in the study, deferred informed consent will be sought from the patient within a reasonable timeframe following clinical assessment/treatment (within 72 hours for first contact). Information will be provided and consent sought for the continuation in the study, and for continued use of data obtained. If the patient lacks capacity, a consultee will be consulted as soon as possible and given information about the study. The consultee will advise as to whether the person should take part in the study, and what the person's wishes and feelings about taking part in the project would be if they had capacity to decide (Mental Capacity Act s32) [1]. The consultee does not give consent themselves. The choice of who acts as consultee is important. A consultee should be someone who is close to the patient, is trusted by them, and knows them well enough to advise what their wishes and preferences about participating would be [31]. Informed consent will also be sought from the patient themselves as soon as possible following any regaining of capacity. If the consultee so advises, the participant must not take part and, if already taking part, must be withdrawn. If the person who lacks capacity indicates (in any way) that they wish to be withdrawn from the study, they

must be withdrawn without delay without having to give reasons, if they don't want to and without prejudicing their further treatment. In cases where the participant dies following the intervention, we will continue to use their data. In instances where the original copy of the consent form cannot be obtained, for example due to restrictions on paperwork leaving the bedspace because of confirmed or suspected COVID-19 or use of a continuous positive airway pressure (CPAP) machine, local NHS Trust/Health Board policies will be followed such as taking a photograph of the signed consent form and sending it to the research delivery staff for printing out and filing in the Site File.

The use of anonymous data from deceased persons is lawful, and consent is not legally required from the person before they die or from a nominated representative however a letter informing them of the participants inclusion in the study will be sent along with contact details of the study team if they have further questions. A flowchart for the consent process can be seen in Figure 2.

Figure 2: Participant Consent Flowchart.

Footnotes

1. If participant is discharged, consent obtained as detailed. Delegated HCP to try to obtain consent prior to discharge or Research Team will attempt contact up to three times. If patient is not contactable, they will be removed from study.
2. In extreme circumstances where a personal consultee cannot be identified, ED staff to approach a nominated consultee who has knowledge of participant's previous care but no involvement in the PRONTO trial.
3. If a participant dies prior to obtaining consent, the family will be informed via letter with study contact details and further information.

We will also pay particular consideration to how the information about the study is provided, as recent evidence suggests that despite undergoing ethical review, study documents lacked essential information, incorrectly used terminology, and conflated professionals' clinical and representation roles, particularly in emergency research and ICU settings [32]. We will involve our patient focus group in the development of these materials. We will also provide training for all HCPs involved in information giving and taking of consent to ensure they fully understand the research governance frameworks.

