12.1 Withdrawal

In this trial, the intervention used is in addition to current standard practice and poses minimal risk to the patient with the treating clinician retaining oversight on whether or not to adhere to the interventional algorithm. Due to time constraints of managing suspected sepsis

(see section 9.1), patients will be randomised into either the standard care arm or interventional arm on diagnosis with suspected sepsis, prior to consent being obtained. Participants have the right to withdraw consent for use of clinical data collected in any aspect of the trial at any time. The participants' care will not be affected at any time by declining to participate or withdrawing from the trial. Some participants may wish to withdraw the use of the data upon first approach for deferred consent, following the intervention. If a participant provides deferred consent at this stage but subsequently withdraws from the trial, clear distinction must be made as to what aspect of the trial the participant is withdrawing from. These aspects could be:

- i. Partial withdrawal from further data collection (questionnaires, clinical assessments)
- ii. Complete withdrawal from further data collection
- iii. Withdrawal of permission to use data already collected

The withdrawal of participant consent shall not affect the trial activities already carried out and the use of data collected prior to participant withdrawal.

Participants who consent and subsequently withdraw are invited to complete a withdrawal form (see Withdrawal Form in trial pack). If they decline, the withdrawal form should be completed by the researcher/clinician based on information provided by the participant. This withdrawal form should be sent to the trial manager. Any queries relating to potential withdrawal of a participant should be forwarded to the trial manager.

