16.3 Missing, unused & spurious data

Missing primary outcome data is likely to be minimal, so complete case analysis will be used. However, if this exceeds more than 20% of participants we will employ multiple imputation and report the impact on the treatment effect alongside the complete case analysis. Further detail is provided in the PRONTO Statistical Analysis Plan (SAP).

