17.1 Main analysis

The primary analysis will be intention to treat and will fit separate two-level logistic regression models (patients nested within sites) to both primary outcomes (antibiotic initiation and mortality), controlling for baseline NEWS2 score (minimisation factor). The intervention will be considered effective if there is both a significant reduction in antibiotic initiation AND if the difference in mortality between the two group is negligible (i.e. non-inferior). (See section 5.3 for the primary outcome for effectiveness table which includes antibiotics and mortality outcomes.)

A planned interim analysis of the co-primary outcomes will be conducted when 50% of patients have been recruited and followed up for 28 days. Stopping the study shall be recommended by the IDMC based on group-sequential O'Brien-Fleming boundaries [37, 38]. They shall recommend stopping for effectiveness if:

- the PCT guided assessment is superior in terms of 28-day mortality (i.e. a significant reduction to less than 15%), or
- the PCT guided assessment is non-inferior in terms of 28-day mortality and superior in terms of initiation of antibiotics.

They shall recommend stopping for futility if the results of the interim analysis suggest futility for both endpoints.

In case the 28-day mortality rate in the control arm deviates from the assumed 15%, the absolute 2.5% non-inferiority margin will be replaced with an arcsine difference 'non-inferiority frontier' [39].

The final primary analysis will be adjusted to account for the interim analysis. Imputation of missing data will be done as part of sensitivity analyses.

In a secondary analysis, complier adjusted causal effect models will be fitted to allow for non-adherence to the intervention. Two models will be fitted allowing for two different definitions of adherence:

1. Patients randomised to PCT guided care in whom a PCT test is done and the clinician considers the results as part of their decision making.
2. Patients randomised to PCT guided care in whom a PCT test is done and the clinician follows the algorithm exactly.

All secondary analysis will also be performed based on intention to treat and utilising two level models to allow for patients nested within sites. The following analyses will be undertaken (Table 3):

Table 3: Planned outcomes and analyses

Outcome	Measure	Time frame	Analysis
Antibiotic initiation	Time until initiation	In ED	Cox regression

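### Randomised patients who cannot be reached after discharge are removed while those who die are kept, so the analysed set depends partly on the mortality outcome and is not intention to treat

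*Protocol*

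**What the plan says.** Four statements in the protocol bear on who is analysed.

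- **Timing (12.1):** "patients will be randomised into either the standard care arm or interventional arm on diagnosis with suspected sepsis, prior to consent being obtained".
- **What deferred consent covers (9.3):** "Information will be provided and consent sought for the continuation in the study, and for continued use of data obtained". Consent thus governs data already collected as well as further follow-up.
- **Patients who cannot be reached (9.3, footnote 1 to Figure 2):** after discharge the research team tries up to three times, and then "If patient is not contactable, they will be removed from study".
- **Patients who die (9.3):** "In cases where the participant dies following the intervention, we will continue to use their data". Footnote 3 adds: "If a participant dies prior to obtaining consent, the family will be informed via letter with study contact details and further information".

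On analysis, section 17.1 states: "The primary analysis will be intention to treat". Section 16.3 states: "Missing primary outcome data is likely to be minimal, so complete case analysis will be used", with multiple imputation if more than 20% of participants lack the outcome. No section reconciles the removal rule with the intention-to-treat label, or says that outcomes from routine records are kept for patients who could not be contacted.

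**The concern.** Removal takes place after randomisation and after the intervention. Take two patients who have not given deferred consent: one goes home and does not answer, the other dies. The first leaves the study and the second stays. Retention among non-consenters is therefore tied to a co-primary outcome, and the remaining set is not everyone randomised.

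This matters most for the mortality comparison, which rests on a 2.5-point non-inferiority margin. Unequal removal is plausible. The trial is open label, discharge is the route to removal, and the economic plan (section 18.2) counts fewer admissions among the expected savings. If patients sent home without IV antibiotics are removed more often, the antibiotic endpoint could be affected too. The rules in 16.3 may not help, because a removed patient may never be counted as having a missing outcome.

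**Working it through.** **The plan's own figure.** Inputs from section 16.2: mortality 15% in both arms, margin 2.5 points, one-sided 5%, power 90%.

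n per arm = (1.645 + 1.282)² × 2 × 0.15 × 0.85 / 0.025² ≈ 3495, so 6990 in total against 7002 stated (0.2% lower). Dropout: 7002 / 0.95 = 7371 against 7372 stated. Ratio 7676 / 7372 = 1.041, as stated. The sample-size arithmetic is not at fault.

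**Apparent mortality under the removal rule.** Let p be true mortality and r the share of survivors removed, with all deaths kept. Then

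apparent mortality = p / [p + (1 − p)(1 − r)].

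The protocol gives no value for r. The range 0 to 20% per arm is an assumption. With p = 15%:

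| r | Calculation | Apparent mortality |
|---|---|---|
| 0% | 0.15 / 1 | 15.0% |
| 5% | 0.15 / 0.9575 | 15.7% |
| 10% | 0.15 / 0.915 | 16.4% |
| 15% | 0.15 / 0.8725 | 17.2% |
| 20% | 0.15 / 0.83 | 18.1% |

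**False difference when true mortality is 15% in both arms.**

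- Equal removal: 0.
- 5% against 10%: 0.73 points.
- 10% against 15%: 0.80 points.
- 15% against 20%: 0.88 points.

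A 5-point gap is therefore worth 0.7 to 0.9 points, or 29% to 35% of the margin. The sign depends on which arm loses more survivors.

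**Effect on the conclusion.** Chance of declaring non-inferiority = Φ[(0.025 − d)/SE − 1.645], where d is the apparent difference (PCT minus control) and SE is the unpooled standard error from the patients left out of 7676 randomised. The interim look is ignored and the margin is held at 2.5 points.

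| True mortality, PCT / control | Survivors removed, PCT / control | d (points) | Chance of declaring non-inferiority |
|---|---|---|---|
| 15% / 15% | 0 / 0 | 0 | 92% |
| 15% / 15% | 5% / 5% | 0 | 90% |
| 15% / 15% | 10% / 10% | 0 | 88% |
| 15% / 15% | 10% / 5% | +0.7 | 66% |
| 15% / 15% | 20% / 15% | +0.9 | 53% |
| 17.5% / 15% | 0 / 0 | +2.5 | 5% |
| 17.5% / 15% | 5% / 10% | +1.9 | 18% |
| 17.5% / 15% | 15% / 20% | not tabulated | 15% |

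**How much loss the protocol tolerates.** The dropout allowance is 5% (16.2). The pilot rule passes a consent rate just above 85% of those randomised (section 13, Table 2), and 13.1 considers 50 to 70% consent. These figures include refusals, so they are not non-contact rates. As an outer case, if 15% of all randomised were removed and all were survivors, r = 0.15 / 0.85 = 17.6%. Apparent mortality is then 17.6% and, with equal arms, power is 84%.

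**Side effect on the margin.** Section 17.1 replaces the fixed margin with an arcsine frontier if control mortality departs from 15%. An apparent 16.4% (10% removal) gives a margin of about 2.6 points, a small change.

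**The case against.** **The word removed is not defined.** The sentence is a footnote to a figure that is not shown. Section 12.1 separates stopping data collection from withdrawing data already held, and says that withdrawal does not affect use of data collected before it. This stands in part: exclusion of the data is an inference. It is nevertheless the natural reading, because 9.3 makes use of data already obtained part of what is consented to.

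**Only survivors leave.** A reader might infer this, but footnote 1 says patient. Someone removed early who later dies at home could also be lost, so the premise that all deaths are kept is an assumption.

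**Both co-primary results are biased.** A reader might infer this too, and the documents do not support it. With equal true mortality, equal removal gives no false difference. Fewer admissions appear only as an expected economic saving; the stated aim concerns antibiotic initiation and time to decide.

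**The plausible mechanism is conservative.** If PCT-guided care sends more patients home, more PCT survivors are removed, apparent PCT mortality rises, and non-inferiority becomes harder to show. That is fair. The documents suggest no mechanism for the opposite direction, though they do not exclude it.

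**Large removal rates look unlikely.** Verbal agreement precedes randomisation (9.1), staff try to obtain consent before discharge, and hospitalisation is normal in this population (section 15). The pilot criteria also use the number randomised as denominator, so large losses would be noticed. This argues against the extreme scenarios but does not repair the label.

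**The deceased differ in law.** Section 9.3 gives a legal reason for using their data and none for living patients without consent. This stands, so retention cannot be assumed to be permitted.

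**Sensitivity analyses belong in the SAP.** Agreed: their absence from the protocol is not a fault. The removal rule and the label are in the protocol, however, and a SAP cannot analyse data that the study may not use.

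**Conclusion.** The point holds in a limited form. As written, the rules make retention among patients without deferred consent depend partly on 28-day mortality, and the resulting set is not the intention-to-treat set named in 17.1. That part rests on the text and on the natural reading of removal.

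Size and direction of bias are unknown. With equal removal and equal true mortality the cost is a higher apparent event rate and lower precision. With a 5-point gap between arms in the share of survivors removed, the mortality difference shifts by 0.7 to 0.9 points. Depending on direction, power falls from 92% to between 53% and 66%, or the chance of a false non-inferiority claim rises from 5% to between 15% and 18%. These figures assume removal rates that the protocol does not give, retention of all deaths, a fixed margin and no interim look. The effect on the antibiotic endpoint is possible but not quantified. It would be wrong to conclude that the trial's result is biased, or biased towards a claim of safety.

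**What to change.** 1. Subject to ethics and confidentiality approval, amend footnote 1 so that a patient who has not refused but cannot be reached stays in the randomised arm with routinely recorded 3-hour antibiotic and 28-day vital status data. Remove patients only on refusal or consultee advice. Neither co-primary outcome needs patient contact: Table 1 in section 11.1 takes both from charts and notes, and section 23.2 foresees tracing through NHS Digital.
2. If approval is not given, stop calling the analysis set intention to treat and describe it as what it is.
3. In either case, report removals by arm, site and NEWS2. Pre-specify a sensitivity analysis that restores removed patients to their randomised arm as alive at 28 days. Add a tipping-point analysis by arm, which also covers deaths missed after removal. If the SAP already contains these, a cross-reference is enough.

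The cost is one amendment with ethics review and a little extra analysis, using arm, site and NEWS2, which randomisation already requires.
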